Abbreviated Title: Ad5-based combination vaccines
Version Date: 05.16.2018

Abbreviated Title: Ad5-based combination vaccines

CC Protocol #: 18C0032 A

Version Date: May 16, 2018

IBC#: RD-17-VIII-13

OSP#: 1712-1703

NCT #: NCT03384316

Title: Phase I Trial Using a Multi-Targeted Recombinant Ad5 (CEA/MUC1/Brachyury) Based Immunotherapy Vaccine Regimen in Patients with Advanced Cancer

NCI Principal Investigator: [name]
Laboratory of Tumor Immunology & Biology (LTIB),
CCR, NCI
[name]
[name]
[name]
[contact]
Email: [contact]

Investigational Agents:

Drug Name:	ETBX-011; adenoviral CEA vaccine	ETBX-061; adenoviral MUC1 vaccine	ETBX-051; adenoviral brachyury vaccine
IND Number:	17676	17676	17676
Sponsor:	Center for Cancer Research	Center for Cancer Research	Center for Cancer Research
Manufacturer:	Etubics	Etubics	Etubics

PRÉCIS

Background:

- The overall goal of the current project is to expand our immunotherapeutic approach for the treatment of advanced cancer employing a multi-targeted approach.
- Therapeutic cancer vaccines targeting overexpressed proteins offer a potential method to activate T cells against tumors.
- A novel adenovirus based vaccine targeting three (3) human tumor associated antigens (TAA), CEA, MUC1, and brachyury, respectively has demonstrated anti-tumor cytolytic T cell responses in pre-clinical animal models of cancer.

Objectives:

- To determine the overall safety and recommended phase 2 dose of a combination of three immunotherapeutic vaccines (ETBX-011/ETBX-061/ETBX-051), when administered subcutaneously (SC) to subjects with advanced solid tumors

Eligibility:

- Subjects age 18 and older with cytologically or histologically confirmed locally advanced or metastatic solid tumor malignancy who have completed or had disease progression on at least one prior line of disease-appropriate therapy or who are not candidates for therapy of proven efficacy for their disease.
- Subjects may have measurable or non-measurable but evaluable disease. Subjects with surgically resected metastatic disease at high risk of relapse are also eligible.
- ECOG performance status ≤ 1
- Adequate organ and bone marrow function
- Subjects with active autoimmune diseases requiring systemic treatment and subjects requiring systemic steroids (except for physiologic doses for steroid replacement) are not allowed

Design:

- This is a Phase I trial in subjects with advanced cancer. A combination of three therapeutic vaccines (ETBX-011, ETBX-51, EBX-61) using the same modified Adenovirus vector backbone, separately encoding three well-studied tumor-associated antigens will be assessed. The vaccine will be tested at a single dose level, and a dose de-escalation design (if required). The dose level of each vaccine tested will be 5×10^{11} VP. This dose has been found in prior phase 1 testing of Ad5 [E1-, E2b-]-CEA(6D) (ETBX-011) to be well tolerated (with no dose-limiting toxicities (DLTs) or related Serious adverse events (SAEs), and optimal for induction of immune responses. Each of the three vaccines will be administered subcutaneously (SC) at separate injection sites (proximal limb, preferably the thigh), every 3 weeks for 3 doses, then bi-monthly (every 8 week) boosts for up to a year.
- Up to six patients will be enrolled at Dose Level 1. If ≤ 1 of 6 patients experience a DLT, initiation of the dose expansion phase will occur. If ≥ 2 of 6 experience DLT at Dose Level 1, then dose de-escalation will occur. Up to six patients will be enrolled at the lower dose level Dose Level -1 (1×10^{11} VP). If ≤ 1 of 6 patients experience a DLT, then the maximum tolerated (MTD) will be declared at this dose, and initiation of the dose expansion phase

will occur. If ≥ 2 of 6 experience DLT at Dose Level -1, then a protocol amendment may be written to evaluate a further dose de-escalation.

- A dose expansion phase of study will be enrolled after the MTD of the combination vaccine has been determined. An additional 4 subjects will be enrolled in the dose expansion component of the trial, for a total of 10 subjects at the MTD.
- The ETBX-011, ETBX-51 and ETBX-61 vaccines will be administered SC every 3 weeks for 3 doses, and then bi monthly boosts for up to a year. Evaluations including immunological assessments will be carried out at baseline, on days of vaccination, and after the last vaccination.

TABLE OF CONTENTS

PRÉCIS 2

TABLE OF CONTENTS.....	4
1 INTRODUCTION.....	12
1.1 STUDY OBJECTIVES AND ENDPOINTS.....	12
1.1.1 Primary Objectives.....	12
1.1.2 Secondary Objectives.....	12
1.1.3 Exploratory Objectives.....	12
1.1.4 Primary Endpoints.....	12
1.1.5 Secondary Endpoints.....	12
1.1.6 Exploratory Endpoints.....	12
1.2 BACKGROUND AND RATIONAL.....	13
1.2.1 Overall Objective.....	13
1.2.2 Brachyury Expression in Cancer and Its Use as an Immunotherapy Target.....	13

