1.1.5 Secondary Endpoints

- Objective response rate (ORR; confirmed complete or partial response) according to the Response Evaluation Criteria in Solid Tumors (RECIST) Version 1.1.
- Disease control rate (DCR; confirmed response or stable disease [SD] lasting for at least 6 months).
- Duration of response.
- PFS
- OS

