2 ELIGIBILITY ASSESSMENT AND ENROLLMENT

2.1 ELIGIBILITY CRITERIA

2.1.1 Inclusion Criteria

- 2.1.1.1 Age \geq 18 years (male and female).
- 2.1.1.2 Ability to understand and provide signed informed consent that fulfills Institutional Review Board (IRB)'s guidelines.
- 2.1.1.3 Subjects with cytologically or histologically confirmed locally advanced or metastatic solid tumor malignancy.
- 2.1.1.4 Subjects must have completed or had disease progression on at least one prior line of disease-appropriate therapy or not be candidates for therapy of proven efficacy for their disease.
- 2.1.1.5 Subjects may have measurable or nonmeasurable but evaluable disease as defined in section 6.3.1. Subjects with surgically resected locally advanced or metastatic disease at high risk of relapse are also eligible.
- 2.1.1.6 Eastern Cooperative Oncology Group (ECOG) performance status \leq 1 ([Appendices](#)
- 2.1.1.7 [Appendix A](#))
- 2.1.1.8 Subjects who have received prior CEA, MUC1, and/or Brachyury-targeted immunotherapy (vaccine) are eligible for this trial if this treatment was discontinued at least 4 weeks prior to enrollment.
- 2.1.1.9 Resolution of clinically significant side effects of prior chemotherapy, radiotherapy, immunotherapy or surgical procedures to NCI CTCAE Grade \leq 1 or grade \leq 2 for neuropathy.
- 2.1.1.10 Adequate hematologic function at screening, as follows:
 - 2.1.1.10.1 Absolute neutrophil count (ANC) \geq 1 x 10⁹/L
 - 2.1.1.10.2 Hemoglobin \geq 9 g/dL
 - 2.1.1.10.3 Platelets \geq 75,000/mcL.

2.1.1.11 Adequate renal and hepatic function at screening, as follows:

2.1.1.11.1 Serum creatinine ≤ 1.5 x upper limit of normal (ULN) OR creatinine clearance (CrCl) ≥ 40 mL/min (if using the Cockcroft-Gault formula below):

i. *Female* CrCl = [(140 - age in years) x weight in kg x 0.85] / [72 x serum creatinine in mg/dL]

ii. *Male* CrCl = [(140 - age in years) x weight in kg x 1.00] / [72 x serum creatinine in mg/dL]

2.1.1.11.2 Bilirubin ≤ 1.5 x ULN OR in subjects with Gilbert's syndrome, a total bilirubin ≤ 3.0 x ULN

2.1.1.11.3 Alanine aminotransferase (ALT) and aspartate aminotransferase (AST) ≤ 2.5 x ULN, unless liver metastases are present, then values must be ≤ 3 x ULN)

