2.1.2 Exclusion Criteria

2.1.2.1 Pregnant and nursing women. Because there is an unknown but potential risk for adverse events in nursing infants secondary to treatment of the mother with combination ETBX-011, ETBX-051, ETBX-061, breastfeeding should be discontinued if the mother is treated with combination ETBX-011, ETBX-051, ETBX-061. These potential risks may also apply to other agents used in this study.

2.1.2.2 There should be a minimum of 4 weeks from any prior investigational drug, chemotherapy, immunotherapy, with the exception of hormonal therapy for prostate and breast cancers, HER2-directed therapy for HER2+ breast or stomach cancer (3+ IHC or FISH+), drugs targeting EGFR, ALK or ROS1 in EGFR, ALK, ROS1-mutated lung cancer, respectively, or standard maintenance therapies for any solid tumor under the condition that subjects are on these therapies for at least two months before start of trial treatment.

2.1.2.3 There should also be a minimum of 4 weeks from any prior radiotherapy except for palliative bone directed therapy.

2.1.2.4 Known active brain or central nervous system metastasis (less than 1 month out from definitive radiotherapy or surgery), or seizures requiring anticonvulsant treatment, or clinically significant cerebrovascular accident or transient ischemic attack (<3 months).

- 2.1.2.5 Subjects with active autoimmune disease requiring systemic immunosuppressive treatment within the past 4 weeks such as but not restricted to inflammatory bowel disease, systemic lupus erythematosus, ankylosing spondylitis, scleroderma, or multiple sclerosis. A history of autoimmune disease which is not active nor has required recent systemic immunosuppressive therapy (< 4 weeks prior to enrollment) is not reason for exclusion.
- 2.1.2.6 Subjects with serious intercurrent chronic or acute illness, such as cardiac or pulmonary disease, hepatic disease, or other illness considered by the Investigator as high risk for investigational drug treatment.
- 2.1.2.7 Subjects with clinically significant heart disease, such as congestive heart failure (class II, III, or IV defined by the New York Heart Association functional classification), history of unstable or poorly controlled angina, or history (< 1 year) of ventricular arrhythmia.

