2.2 SCREENING EVALUATION

All screening tests and procedures must be performed within 28 days prior to the first planned dosing of the study drug, unless otherwise noted. The following procedures and evaluations will be performed and documented in the subject's source records.

- History and physical exam including ECOG performance status and vital signs
- 12-Lead ECG
- Clinical laboratory tests (within 16 days prior to drug administration)
 - Chemistry: sodium, potassium, chloride, bicarbonate, calcium, glucose, BUN, creatinine, ALT, AST, alkaline phosphatase, total protein, albumin, and total and direct bilirubin.
 - Hematology: complete blood count (CBC) with differential and platelets
 - Coagulation panel: PT, INR, and PTT.
 - Urinalysis.
- Serum pregnancy test (β -HCG) for females of childbearing-potential and women < 12 months since the onset of menopause (within 16 days prior to enrollment)
- HBV (HBsAg), HCV (anti-HCV), HIV (anti-HIV) screening (within 3 months prior to enrollment)
- Appropriate tumor imaging and assessment. All baseline tumor measurements should be performed based on the subject's qualifying scan obtained within 28 days prior to the start of treatment.
- Confirmation of diagnosis. A report from any CAP or CLIA certified laboratory is acceptable.

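### Subjects may enter after completing a prior line without progression, so tumour stability that predates the vaccine counts in DCR and PFS, and the planned report would not show it

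*Combined protocol and SAP*

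**What the plan says.** All references are to the combined protocol and SAP.

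- **Entry.** The Précis admits subjects "who have completed or had disease progression on at least one prior line of disease-appropriate therapy", and criterion 2.1.1.4 sets the same rule. Both also accept subjects for whom no treatment of established benefit is suitable. There are three alternative routes, and only one of them involves progression.
- **Other non-progressing entrants.** Criterion 2.1.1.5 adds "Subjects with surgically resected locally advanced or metastatic disease at high risk of relapse are also eligible". Criterion 2.1.2.2 exempts from washout, among others, "standard maintenance therapies for any solid tumor under the condition that subjects are on these therapies for at least two months before start of trial".
- **Washout and baseline scan.** Criterion 2.1.2.2 states "There should be a minimum of 4 weeks from any prior investigational drug, chemotherapy, immunotherapy", without saying whether the interval ends at enrolment or at first dose. Section 2.2 takes baseline measurements from a "qualifying scan obtained within 28 days prior to the start of treatment".
- **Endpoint and clocks.** Section 1.1.5 lists "Disease control rate (DCR; confirmed response or stable disease [SD] lasting for at least 6 months". Section 6.3.6 starts the stable-disease clock at start of treatment, and section 8.4.3.3 starts PFS at first treatment.
- **Reporting.** Sections 8.4.3.1 and 8.4.3.3 present results by dose level and overall. Section 8.4.5 plans no baseline descriptive statistics, section 8.4.7 rules out subgroup analyses because the study is small, and section 8.4.8 rules out tabulating individual data.

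**The concern.** In a single-arm trial, six months of stable disease suggests drug activity only if the tumour would otherwise have been expected to progress in that time. A subject who finished a prior line in stable disease or response, is off therapy and has residual tumour is eligible. If the tumour simply stays as it was, that subject becomes a disease control and contributes a long PFS time.

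The trial's own reporting would not let anyone detect this. Two reports with the same DCR, one from subjects who were all progressing and one from subjects mostly stable at entry, would look identical. Section 1.2.1 names efficacy among the things this trial is to test, and sections 1.2.1 and 1.2.9 foresee later combination trials. The DCR and PFS figures should therefore be readable, even though they are preliminary.

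**Working it through.** **1. The plan's own figures.** Section 8.2 gives 6 to 12 subjects for dose finding plus 4 in expansion, so 10 to 16 treated. With 16 assumed screen failures the maximum is 16 + 16 = 32, as stated. The number at the MTD is 6 + 4 = 10, also as stated. The plan gives no reference rate, threshold or test for DCR or PFS.

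**2. When 6-month stability is shown.** Section 6.3.1 and the study calendar put scans at weeks 6, 14, 22, 30 and so on. At 4.345 weeks per month, week 22 is 5.1 months and week 30 is 6.9 months. A subject who enters stable and stays stable first meets the DCR definition at the week-30 scan.

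**3. Illustration with no vaccine effect.** Let *a* be the assumed probability of 6-month stability if progressing at entry, *b* the same if not progressing, and *k* the number of 10 subjects not progressing. None of these is in the documents.

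Expected DCR = [*k*·*b* + (10 − *k*)·*a*] / 10.

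For *a* = 0.15 and *b* = 0.50:

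| *k* | Calculation | Expected DCR | P(3 or more controlled) |
|---|---|---|---|
| 0 | (0 + 1.50)/10 | 15% | 0.180 |
| 3 | (1.50 + 1.05)/10 | 25.5% | 0.495 |
| 5 | (2.50 + 0.75)/10 | 32.5% | 0.700 |
| 10 | (5.00 + 0)/10 | 50% | 0.945 |

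The last column is the upper tail of the sum of Binomial(10 − *k*, *a*) and Binomial(*k*, *b*). Three controls is only a yardstick; the plan sets no such cut-off.

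Other assumed pairs at *k* = 5:
- 10%/40%: (2.0 + 0.5)/10 = 25%, against 10% at *k* = 0.
- 20%/60%: (3.0 + 1.0)/10 = 40%, against 20% at *k* = 0.

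**4. A second model.** Take exponential PFS, so 6-month stability is 0.5^(6/median). Assumed medians of 2 to 3 months if progressing give 12.5% to 25%; medians of 6 to 12 months if not progressing give 50% to 71%. With half not progressing, expected DCR is 31% to 48%, a rise of about 12 to 29 percentage points.

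**5. Response.** Table 5 in section 6.3.5 requires a decrease of at least 30% from the baseline sum for a PR, and section 8.4.3.1 counts only confirmed responses. Stability alone cannot meet this.

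**6. Scan and washout.** If washout is counted to first dose, a scan on day −28 after the minimum washout falls 28 − 28 = 0 days after the last prior dose. If it is counted to enrolment, the scan falls later by the enrolment-to-dose gap: 7 days after the last prior dose with a 7-day gap, and 28 days, hence no overlap, with a 28-day gap.

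**The case against.** The strongest reply is that no decision depends on these endpoints. The primary endpoints in section 1.1.4 concern safety, sections 8.1 and 8.4.3 call the efficacy data preliminary, and section 8.4.1 plans only description. That stands, and it limits the weight of the point. It does not make an unreadable DCR useful.

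Section 8.4.7 gives a reason for having no subgroups: the study is small. That is a sound reason against testing or estimating differences, but less so against showing counts. For scale, 3 of 10 has an exact 95% interval of 6.7% to 65.2%, so cells within a split will be very imprecise. Nor does documented progression make stability fully interpretable, since a slow-growing tumour can progress and then stay within stable-disease limits untreated. The split improves interpretation without settling it.

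A reader might infer three stronger things that the documents do not support:

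- **That ORR is inflated to a similar degree.** It would take continued, confirmed shrinkage of at least 30% after the baseline scan, as a late effect of earlier treatment. That is possible but a minor concern.
- **That the baseline scan systematically credits prior therapy to the vaccine.** Full overlap needs the shortest washout, the earliest permitted scan and a washout counted to first dose, which criterion 2.1.2.2 does not state. The bias can also run the other way: growth between an early scan and first dose counts towards the 20% progression threshold.
- **That the calculated rates forecast this trial.** Nothing indicates how many subjects would enter without progression. The denominator of 10 also ignores section 8.3, which restricts response evaluability to re-evaluated subjects with measurable disease.

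**Conclusion.** The point holds for DCR and PFS. Entry does not require progression, both measures run from first vaccination, and no planned output separates or even describes subjects by progression status at entry. Stability that predates the vaccine is therefore mixed with any vaccine effect.

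The direction rests on one assumption: that subjects not progressing at entry stay stable longer than those who are. The size cannot be derived from the documents. Under the assumed 15% and 50%, with 5 of 10 subjects not progressing, expected DCR with an inactive vaccine is about 33% instead of 15%; the other assumptions tried move the figure but not the direction. ORR is little affected, and the primary DLT/MTD objective is unaffected. This is an inexpensive improvement to secondary, preliminary endpoints and does not call the design into question.

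**What to change.** Leave eligibility as it is and add the following to sections 8.4.3.1 and 8.4.3.3.

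- **Classification.** Before outcomes are reviewed, classify each subject as with or without documented progression on or after the most recent anticancer therapy and before first vaccination. The words *on or after* matter: a rule limited to progression since the last therapy would misplace subjects who progressed during that therapy and then stopped it. The source is the prior-treatment and prior-radiology history already taken at screening (study calendar, footnote d). The SAP should also say where subjects with no prior anticancer therapy are placed.
- **Reporting.** Give DCR counts and PFS descriptively for subjects entering with documented progression beside the overall figures, without a test.
- **Interpretation.** State that stable disease of 6 months or more in subjects without documented progression at entry is not read as evidence of vaccine activity.
- **Section 8.4.7.** Name this descriptive split as the one exception.

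The cost is one CRF field, one extra row or column in the tables, and a few lines of SAP text. The drawback is very small cells and a smaller denominator for the more interpretable DCR. Sample size, dosing and the DLT rules do not change.

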LIST OF ABBREVIATIONS AND DEFINITIONS OF TERMS

Abbreviation or Specialist Term	Explanation
β-HCG	β-Human chorionic gonadotropin
Ad	Adenovirus
Ad5	Adenovirus serotype-5
Ad5 [E1-]	Ad5 with deletions in the early 1 (E1) and early 3 (E3) gene regions
Ad5 [E1-, E2b-]	Ad5 with deletions in the early 1 (E1), early 2b (E2b), and early 3 (E3) gene regions
AE	Adverse event
AESI	Adverse event of special interest
ALT	Alanine aminotransferase
AST	Aspartate aminotransferase
BSI	BioSpecimen Inventory
BUN	Blood urea nitrogen
CAP	College of American Pathologists
CBC	Complete blood count
CCR	(NCI) Center for Cancer Research
CEA	Carcinoembryonic Antigen
CLIA	Clinical Laboratory Improvement Amendments
CMI	Cell-mediated immunity
CMV	Cytomegalovirus
CR	Complete response
CRADA	Cooperative Research and Development Agreement
CRF	Case report form
CSC	Cancer stem cell
CT	Computed tomography
CTCAE	Common Terminology Criteria for Adverse Events
DFS	Disease-free survival
DCR	Disease control rate
DLT	Dose-limiting toxicity
DLTs	Dose-limiting toxicities
E1	Adenovirus early 1 gene
E2b	Adenovirus early 2b gene

Abbreviation or Specialist Term	Explanation
E3	Adenovirus early 3 gene
ECG	Electrocardiogram
ECOG	Eastern Cooperative Oncology Group
EGFR	Epidermal growth factor receptor
ELISA	Enzyme-linked immunosorbent assay
EOS	End of study
ETBX-011	Ad5 [E1-, E2b-]-CEA
ETBX-051	Ad5 [E1-, E2b-]-Brachyury
ETBX-061	Ad5 [E1-, E2b-]-MUC1
ETBX-081	Combination of ETBX-011 + ETBX-051 + ETBX-061 Vaccines
FDA	Food and Drug Administration
FFPE	Formalin-fixed paraffin-embedded
GCP	Good Clinical Practice
GLP	Good Laboratory Practice
GM-CSF	Granulocyte-macrophage colony-stimulating factor
cGMP	Current Good Manufacturing Practice
HBV	Hepatitis B virus
HCV	Hepatitis C virus
HHS	Health and Human Services
HIV	Human immunodeficiency virus
HPV	Human papilloma virus
HTD	Highest tested dose
ICH	International Conference on Harmonization
IEC	Independent Ethics Committee
IFN	Interferon
IHC	Immunohistochemistry
IL	Interleukin
INR	International normalized ratio
IRB	Institutional Review Board
ISH	In situ hybridization
LLD	Longest lesion diameter
LLN	Lower limit of normal

Abbreviation or Specialist Term	Explanation
MDSC	Myeloid-derived suppressor cell
MedDRA	Medical Dictionary for Regulatory Activities
MRI	Magnetic resonance imaging
MTD	Maximum tolerated dose
MUC1	A Transmembrane glycoprotein
MUC1c	A modified MUC1 with agonist epitope
NCI	National Cancer Institute
NIH	National Institutes for Health
NK	Natural killer (cell)
ORR	Objective response rate
OS	Overall survival
PBMC	Peripheral blood mononuclear cell
PD	Progressive disease
PFS	Progression-free survival
PR	Partial response
PT	Prothrombin
PTT	Partial thromboplastin time
aPTT	Activated partial thromboplastin time
RECIST	Response Evaluation Criteria in Solid Tumors
SAE	Serious adverse event
SC	Subcutaneous
sCD27	Soluble CD27
sCD40L	Soluble CD40L
SD	Stable disease
SOC	System Organ Class
SRC	Safety Review Committee
SUSAR	Suspected unexpected serious adverse reactions
TAA	Tumor-associated antigen
Treg	Regulatory T cells
ULN	Upper limit of normal
VP	Virus particles

1 INTRODUCTION

1.1 STUDY OBJECTIVES AND ENDPOINTS

1.1.1 Primary Objectives

To determine the overall safety and recommended phase 2 dose of a combination of three immunotherapeutic vaccines (ETBX-011, ETBX-061, and ETBX-051), when administered subcutaneously (SC) to subjects with advanced solid tumors.

1.1.2 Secondary Objectives

To make preliminary assessments of:

- Objective response rate (ORR),
- Disease control rate (DCR),
- Duration of response,
- Progression-free survival (PFS)
- Overall survival (OS)

in subjects with advanced solid tumors treated with the combination ETBX-011, ETBX-051, ETBX-061 vaccine regimen.

